E4.b. Unit of Randomization. We will randomize the study on the provider level. We will use a random number generator to assign offices to study arms, and will employ multi-level hierarchical models to adjust for clustering within the physician level, described in more detail below.

E4.c. Study Design Overview.

We will auto-enroll all eligible patients to participate in the pragmatic trial and will administer baseline questionnaires as further detailed in the Recruitment Procedures and Outcome Measurement sections below. Patients within the physicians randomized to the CDS arm will not receive the PEAT materials; their physicians will receive the Choosing Wisely alerts via the EHR (Epic Systems, Verona, Wisc.) when appropriate. Patients within the physicians randomized to PEAT will receive the engagement materials via REDCap two days prior to their PCP office visit, supplemented by duplicate paper copies sent via express delivery. For both study arms, patients will receive Clinician and Group Consumer Assessment of Healthcare Providers and Systems (CG-CAHPS) one day after their office visit. They will receive the PROMIS questionnaires every month throughout the study period. We will track follow-up visits through the EHR reports. In all instances, patients may refuse to participate by either not using the PEATs sent via REDCap, or not completing outcome questionnaires.

3. Analysis, Dissemination, and Implementation. In Year 3, we will conduct the statistical analyses and will collaborate with our patient partners to determine the implications of the study results. We present our Dissemination and Implementation plan in full detail below.

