E4.d. Recruitment Procedures (PC-2). Patients meeting inclusion criteria who are managed by one of the 80 participating PCPs at the Cedars-Sinai Medical Network will be auto-enrolled in the study. Patients will receive a written notification via mail of their inclusion in the study and at that time they will be told about the study details, including research procedures and requirements for follow-up, as well as the risks and benefits of study participation. At this time, patients will have the opportunity to actively opt out of receiving the education materials (if they are randomized to PEAT arm). Patients who do not opt out will receive education materials and their care will proceed as usual. Patients who are passively enrolled will receive the study questionnaires via REDCap. We estimate that out of the 4,000 patients eligible for the study (calculated from a quality improvement project based on claims data), approximately 30% will complete all of the questionnaires, which is in line with our sample size calculations. Once the patients complete monthly questionnaires, we will provide a \$5 gift card for filling out the enrollment survey. We have budgeted \$25 per patient as

a financial incentive for completing the questionnaires (Appendix I, **Table 1 for Recruitment Plan** and **Table 2 for Passive Enrollment Estimates**).

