E5.c. Power Calculations. Guided by previous work in chronic pain interventions,¹⁴⁰ we calculated sample size using an intracluster correlation coefficient of 0.02, an α level of 0.05, 90% power, and detection of a mean (SD) difference of 0.3 standard deviations on the PROMIS Pain Interference scale. We calculated a sample size of 320 patients per study arm, for a total of 640 patients. To compensate for predicted loss to follow-up, multiple variables in the final multi-level models, as well as sub-group analyses, we inflated the sample size by 50% to 960. Since we will be examining the effect of the interventions on a variety of sub-groups within the study sample, such as diagnoses of mental health conditions, race, ethnicity, gender, and chronic pain diagnosis, we will be adequately powered to detect meaningful differences. In our original proposal, we calculated a sample size of 320 patients per study arm for a total of 640 patients. To compensate for predicted loss to follow-up and non-response we had inflated the recruitment target size by 50% to 960. Under the current modification – and given the absence of changes to the assessment schedule, the estimated intracluster correlation coefficient, and the expected mean difference - the sample size required to adequately power the analysis remains unchanged. We believe the recruitment target will also remain consistent, and potentially even fall due to the ability of study staff to call passively enrolled patients and remind them to respond to assessments. We therefore anticipate being adequately powered to detect meaningful differences between the two arms.

E6 Heterogeneity of Treatment Effect (HT-1, HT-3, HT-4)

After reviewing the literature and consulting with our patient partners, we identified specific subgroups we plan to analyze to identify whether there is a heterogeneity of the treatment effects. Below we detail our planned sub-group analyses, our hypotheses, and our plans for statistical analysis for each subgroup. In order to address the problem of multiplicity, a Bonferroni correction will apply to all analyses.

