E7. Data Source Adequacy (IR-1). We plan to collect several types of data for this study. For the PROs, we will collect data directly from patients through web-based questionnaires. We will collect some data on comorbidities and medication use through data collected for clinical care and billing purposes through the EHR. Given that this data is not collected for research purposes, errors, particularly with regards to ICD-10 codes, are possible. We will work with our data warehouse to ensure that the data are cleaned prior to analysis and our statistical analysis team, led by [name], who has experience with clinical data collection and analysis,¹⁴¹ will also conduct extensive exploratory data analysis to identify potential errors in the data.

E7. Missing Data

a. Methods to Prevent and Monitor Missing Data. We anticipate two sources of missing data: the failure of patients to complete the initial set of questionnaires and the loss of patients to follow-up. Monitoring of missing questionnaire data will occur in real-time as online questionnaires are completed, completed partially, or never started. For enrolled patients who do not respond to the questionnaires after baseline, we will conduct two follow-up phone calls to attempt to collect data. After the intervention study period has ended, we will attempt one last follow-up phone call with a sub-sample of non-respondents to see if they are similar to respondents (MD-1). If so, for the hierarchical linear model, maximum likelihood estimation will be consistent as long as the data are missing at random (MD-3).¹³⁷ We are aware of the potential between failure to complete survey elements, failure to use the educational tools, and reduced HRQOL. These hypothesized patterns will receive close scrutiny in the analysis of the mechanisms.

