Attachment C-R: Milestone Schedule

	Milestone Name	Description	Projected Completion Date
A	Project Start Date	-	3/13/2017
B1	Stakeholder engagement meeting	Stakeholder engagement kick-off meeting	3/30/2017
B2	Patient eligibility data pulls	EIS Data Analyst to create a list of eligible patient population	4/30/2017
B3	Study protocol completed	Final trial protocol completed - submit a copy to PCORI	5/30/2017
B4	Patient eligibility data pulls	EIS Data Analyst to finalize list of eligible patient population and other data pulls	5/30/2017
B5	IRB Approval Obtained	Obtain IRB approval for study and submit approval letters to PCORI	7/30/2017
B6	DSMB Meeting 1	Set safety protocols and standards for data safety monitoring	7/30/2017
B7	Integration of questionnaires into patient portal	EIS Data Analyst to integrate questionnaires into MyCSLink	7/30/2017
B8	Select and register project at appropriate site for the study design (Clinicaltrials.gov, RoPR, or other as approved by PCORI before study start date)	Study Identification Number and the Primary Research Completion Date must be sent to PCORI.	7/30/2017
B9	Randomization of clinic sites	Randomization of Cedars-Sinai network offices completed; 50% to CDS arm and 50% to PEAT arm of trial	7/30/2017
B10	Passive patient recruitment begins	Passive data enrollment begins for study participants (N=960) / Study begins	8/1/2017
B11	Pharmacy data collection begins	EIS Data Analyst to begin pull data for passively enrolled patients on pharmacy data for data monitoring purposes	8/1/2017
B12	Patient baseline questionnaires	Enrolled patients begin filling out PROMIS patient reported outcome questionnaires	8/1/2017
B13	Stakeholder engagement meeting	Stakeholder engagement meeting to update on IRB submission and patient eligibility protocols and baseline data collection	8/31/2017
B14	Engagement Update	For the 6-month time intervals (i.e., 6 months, 18 months, 30 months, etc. but not at 12 months or 24 months), provide specific examples of the impact of engagement on project activities during the reporting period. Report this in the Engagement Report section of the PCORI interim progress report.	9/13/2017
B	Report Submission	Submit 6-month Interim Progress Report, Using PCORI Interim Progress Report Template	9/13/2017
C1	Study intervention begins	Study intervention begins	1/1/2018
C2	Stakeholder engagement meeting	Updates on study implementation	2/28/2018

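### Maximum likelihood is the only estimator named, with no small-sample reference for the cluster-level arm contrast: a small excess of type I error with 80 PCPs, a larger one if few offices are randomised

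*Combined protocol and SAP*

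**What the plan says.** Section E5.b of the project plan (Attachment A-R1) describes hierarchical linear growth models with clustering at patient, provider and office level, and says that both fixed and random effects will be tried. It does not say how the variance components are estimated, which distribution the arm coefficient is referred to, or how degrees of freedom are obtained.

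An estimator appears once, in part a of the missing-data section (E7): "for the hierarchical linear model, maximum likelihood estimation will be consistent as long as the data are missing at random".

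The randomised unit is given in two ways. Section E4.b states "We will randomize the study on the provider level", but its next sentence assigns offices to arms. Milestone B9 in Attachment C-R reads "Randomization of Cedars-Sinai network offices completed; 50% to CDS arm and 50% to PEAT arm of trial". Section E4.d refers to "Patients meeting inclusion criteria who are managed by one of the 80 participating PCPs", and the number of offices is not given.

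For sample size (section E5.c), "we calculated sample size using an intracluster correlation coefficient of 0.02, an α level of 0.05, 90% power", with "detection of a mean (SD) difference of 0.3 standard deviations on the PROMIS Pain Interference scale". The result: "We calculated a sample size of 320 patients per study arm, for a total of 640 patients". Then "we inflated the sample size by 50% to 960".

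**The concern.** Every patient of a given PCP (or office) is in the same arm. The standard error of the arm effect therefore comes from variation between clusters, and the information about that variation comes from the number of clusters, not patients. Maximum likelihood (ML) estimates the variance without allowing for the fixed effects being estimated, so it is biased downward. Restricted maximum likelihood (REML) makes that allowance and is equally usable when data are missing at random. Consistency, the property that the plan cites, holds in large samples and does not protect a test based on a limited number of clusters. A normal reference adds to the problem because it ignores the uncertainty in the estimated variance.

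If both apply, intervals for the arm effect are too narrow and the stated 5% level is exceeded, more so with fewer clusters. When the PCP is the cluster, physician gender and years of practice are cluster-level terms too, so their tests rest on the same variance.

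**Working it through.** **Clusters implied by the sample size.** Inputs from E5.c: difference 0.3 SD, alpha 0.05 (taken as two-sided), power 90%, ICC 0.02.

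- Unclustered n per arm = 2 × (1.960 + 1.282)² / 0.3² = 233.5.
- 320 / 233.5 = 1.370 = 1 + (m − 1) × 0.02, so m = 19.5 patients per cluster.
- 640 / 19.5 = about 33 clusters; 16 per arm × 20 patients gives exactly 320 per arm.

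The stated 320 is thus reproduced with about 32 clusters. It is not reproduced with 80 PCPs: m = 8 gives 234 × 1.14 = 267 per arm, and m = 12 gives 234 × 1.22 = 285.

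**Why ML understates the standard error.** Take K equal clusters of m patients, one outcome per patient. The variance of a cluster mean is λ = σ²_b + σ²_e/m, and the arm difference has variance 4λ/K. With SSB the sum of squares of cluster means about their arm means, REML estimates λ by SSB/(K − 2) and ML by SSB/K. The ML standard error is therefore √((K − 2)/K) times the REML one. While the estimated σ²_b is positive, ML with z has type I error P(|t on K − 2 df| > 1.96 × √((K − 2)/K)):

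- K = 80: 1.96 × 0.987 = 1.935 on 78 df, 5.7%
- K = 32: 1.96 × 0.968 = 1.898 on 30 df, 6.7%
- K = 20: 1.96 × 0.949 = 1.859 on 18 df, 7.9%
- K = 10: 1.96 × 0.894 = 1.753 on 8 df, 11.8%

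**Simulation.** At a low ICC the estimated σ²_b is sometimes zero, which pulls these values down. Simulated type I error under no effect, balanced clusters, ICC 0.02 to 0.05, 640 to 960 patients:

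| Clusters | ML, z | ML, t(K−2) | REML, z | REML, t(K−2) |
|---|---|---|---|---|
| 80 (PCPs, E4.d) | 5.3–5.7% | 4.9–5.3% | 5.1–5.4% | 4.7–5.0% |
| 32 (implied by E5.c) | 6.2–6.8% | 5.3–5.7% | 5.6–6.0% | 4.7–5.0% |
| 20 (assumed offices) | 7.2–7.9% | 5.5–6.2% | 6.1–6.6% | 4.6–5.0% |
| 10 (assumed offices) | 10.3–11.7% | 5.9–7.2% | 7.8–8.5% | 4.3–5.0% |

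**Unequal cluster sizes** (coefficient of variation 0.7, assumed; ICC 0.02). ML with z gives 5.6–5.9% at 80 clusters and 7.0–7.2% at 32. REML with t(K−2) gives 5.0–5.1% and 5.1–5.3%.

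**Two physician-level covariates added** (PCP as cluster, balanced). ML with z gives 5.5–5.9% at 80 and 6.9–7.6% at 32. REML with t on clusters minus fitted terms gives 4.8–5.0% and 4.6–5.0%.

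**The case against.** The strongest reply is that the plan does not commit to ML for the arm test. The sentence in E7 is a conditional remark about incomplete data, it is compatible with REML, and E5.b is silent. That stands. A reader might infer that the primary test as planned exceeds 5%. The documents do not support that, because it needs both an ML fit and a normal reference, and neither is specified for this test. What remains is an omission: nothing in the text rules out that combination, and the choice is left to a software default or to the analyst.

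Second, ML is only part of the cause. At 32 clusters REML with z still gives 5.6–6.0%, and ML with t gives 5.3–5.7%. This also stands, and it is why the degrees-of-freedom method matters as much as the estimator.

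Third, the only cluster count stated is 80 PCPs, where the excess is below one percentage point. The figure of about 32 is solved back from a cluster size that E5.c does not give, and it need not be the number analysed. A reader might also infer that error near 10% is to be expected. That arises only at about 12 clusters or fewer, a count the documents do not contain. It cannot be excluded either, since E4.b and milestone B9 both say that offices are assigned.

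Fourth, section E6 promises a Bonferroni correction for all analyses, without a divisor. If each of the two primary models were tested at 0.025 (an assumption), ML with z would give 2.8–3.1% at 80 clusters and 3.6–4.2% at 32. That is below 5% but still above the nominal 2.5%: dividing alpha lowers the level and leaves the relative inflation in place.

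Fifth, the simulation is simpler than the planned monthly growth model with provider and office levels. This is a real limit. It also means that no figure can be given for CG-CAHPS specifically, as the plan's ICC of 0.02 is tied to Pain Interference.

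**Conclusion.** The point holds as a gap in specification with a conditional cost. ML is the only estimator named, and no small-sample reference is given for a contrast between clusters. If ML is used with a normal reference, the excess over 5% is under one point with 80 PCPs, and between one and just over two points at about 32 clusters (the upper end with unequal sizes). It is roughly two to seven points if only 10 to 20 offices are randomised. REML with t on K − 2 stays between 4.3% and 5.0% in every balanced setting tabulated.

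These figures assume one outcome per patient, a single cluster level and an ICC of 0.02 to 0.05. The office counts and the variation in cluster size are assumptions. The point is minor if the PCP is the randomised unit. It matters more if the office is, and the documents do not settle which.

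**What to change.** State the unit actually randomised and the number of clusters. Then add one sentence to E5.b: Models 1 to 3 are fitted by restricted maximum likelihood, and arm and physician-level terms are tested with Kenward-Roger or Satterthwaite degrees of freedom (or, for arm, t on the number of clusters minus 2), at the level of the randomised unit. The missing-data remark in E7 can name restricted maximum likelihood instead, since the missing-at-random argument carries over.

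The cost is a software option and slightly wider intervals. Moving from ML with z to REML with t multiplies the interval width by (1.991/1.960) / 0.987 = 1.03 with 80 clusters and by (2.042/1.960) / 0.968 = 1.08 with 32.

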E4.e. Data Collection (RQ-2). Upon auto-enrollment, we will extract the following variables from the electronic health record: chronic pain condition, length of time with chronic pain diagnosis, race and ethnicity, language, marital status, history of pharmacologic treatment, surgical history related to chronic pain condition, past injuries related to chronic pain condition, and length of time with current primary care provider¹³⁷. When the intervention period is initiated, all eligible patients who have any follow-up visits during this 12-month period in both study arms will be sent the questionnaires. We will also capture depression scores via the Patient Health Questionnaires -PHQ-2 and/or PHQ-9 in the EHR. Furthermore, to determine if conversations about opioid medications took place during the visit that was

informed by either the CDS or the PEATS, we will conduct a structured review of a random sample of charts from both study arms.

E5. Statistical Analysis

E5.a. Descriptive and Exploratory Analyses. We will use frequencies and means for univariate descriptive analyses. We will use chi-square tests and paired t-tests to determine whether there are differences between the two study arms; using these bivariate analyses, we will identify covariates and patient- and physician-level moderators to use in the regression models. We will also consult with our Patient Partner to ensure that all appropriate patient-level covariates are included in the final models.

E5.b. Multi-Variate Regression Models. To evaluate the effectiveness of the comparators on the selected outcomes, we will use hierarchical linear regression models to measure changes in the outcomes over time using growth modeling statistical techniques¹³⁸ and will adjust for clustering at the patient, provider, and provider office level. Growth modeling allows the testing of individual differences in outcomes over time. In this study, we will examine HRQOL and communication scores over 12 months for the two study arms. We will adjust for patient- and provider-level covariates to account for potential confounders and also to identify whether there is heterogeneity of the treatment effect (see below). The proposed models are outlined here. We will test both fixed effects and random effects.¹³⁹ (IR-3):

Primary Outcome: Model 1: Hierarchical Linear Model (Longitudinal Analysis)

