b. Statistical Methods to Handle Missing Data and Sensitivity Analyses. If the data is not missing at random, we will use multiple imputation techniques to impute missing data for respondents (MD-2). We plan on using the *mi impute mvn* command in Stata and will generate 20 datasets compatible with the regressions planned for the final analyses. To insure that the imputation has proceeded as expected, we will visually inspect parameters from successive iterations of the model to determine if they have reached a stationary distribution. We will conduct sensitivity analyses with the dataset that includes imputed data as well as with a dataset that does not include imputed data to determine the effect of the multiple imputation and plan on reporting both results. These precautions will serve to identify autocorrelation in the imputed data and allow for proper maintenance of uncertainty in imputed values (MD-3).

c. Reporting Reasons for Dropout and Missing Data. We will drop data from patients who do not have any visits with their PCP during the intervention period or are lost to follow-up, but will compare descriptive statistics for these patients to patients with at least one visit to their PCP for sensitivity analysis (MD-4, MD-5).

E9. Project Milestones and Timeline.

During the first 3-6 months of the study project, we will train the project staff, refine the study protocol, develop the data dictionaries, and obtain IRB approval. We will hold monthly meetings with our patient partners to finalize the study design and discuss issues related to IRB approval. In Year 1, Q4, we will passively enroll eligible patients in the two study arms. In the 4 weeks before the intervention period, we will send baseline questionnaires via REDCap. In Year 2, we will begin the intervention. We will conduct weekly reports from our EHR data warehouse to determine enrolled patient visits. Enrolled patients will be sent CG-CAHPS survey one day after each primary care visit. Enrolled patients will also receive the PROMIS questionnaires once a month. We will perform monthly checks to assess the completeness of data to minimize missing data and will complete one set of interim data analyses in Year 2 to assess whether there are any issues with missing data. Full data analysis will

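### The imputation that E7.b reserves for data not missing at random itself assumes missing at random; even if the trigger is only misworded, nothing planned re-estimates the arm effect under informative missingness

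*Combined protocol and SAP*

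**What the plan says.** E7 Missing Data, part a, bases the primary analysis on the hierarchical linear model, for which "maximum likelihood estimation will be consistent as long as the data are missing at random". The check offered on that condition is a contact after the intervention period: "we will attempt one last follow-up phone call with a sub-sample of non-respondents to see if they are similar to respondents". The same paragraph names a specific worry: "We are aware of the potential between failure to complete survey elements, failure to use the educational tools, and reduced HRQOL". It promises that these patterns will be looked at closely, without naming an analysis.

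Part b gives the response if the condition fails: "If the data is not missing at random, we will use multiple imputation techniques to impute missing data for respondents". It names the Stata command for multivariate-normal imputation, sets 20 datasets and describes a visual convergence check. It then says: "We will conduct sensitivity analyses with the dataset that includes imputed data as well as with a dataset that does not include imputed data", with both results to be reported.

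Part c adds: "We will drop data from patients who do not have any visits with their PCP during the intervention period or are lost to follow-up". These patients are to be compared descriptively with patients who had at least one PCP visit.

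The outcomes concerned are longitudinal. E5.b says: "In this study, we will examine HRQOL and communication scores over 12 months for the two study arms". E4.c sends the PROMIS questionnaires monthly and CG-CAHPS after office visits, and sends the educational materials to the PEAT arm only.

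**The concern.** Without a shift, multivariate-normal imputation draws the missing scores from a model fitted to the observed ones. It therefore relies on MAR, as the mixed model does. As written, the plan answers a failure of MAR with a second method that needs MAR.

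The plan gives its own reason to take that failure seriously: it suspects that non-completion, non-use of the tools and worse quality of life go together. Only one arm receives the tools, so a missingness process that differs by arm is plausible. That last step is an inference; the plan does not state it. If it were so, the Pain Interference contrast would be biased, and no planned analysis would show how much the conclusion depends on it.

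**Working it through.** **1. The assumption behind each planned step**

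| Step | Where | Re-estimates the arm effect under MNAR? |
|---|---|---|
| Mixed model by maximum likelihood | E7.a | No; assumes MAR |
| Multivariate-normal imputation, no shift described | E7.b | No; assumes MAR |
| Imputed versus non-imputed results | E7.b | No; neither side models MNAR |
| Calls to a sub-sample of non-respondents | E7.a | No; used to judge similarity |
| Close look at the suspected patterns | E7.a | No analysis stated |
| Descriptive comparison of dropped patients | E7.c | No |

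The supplied text contains no delta, pattern-mixture, selection-model or tipping-point analysis.

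**2. The plan's own figures**

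The plan states no figure for bias from missing data. E5.c gives 0.3 SD, ICC 0.02, α 0.05 (taken as two-sided), 90% power, 320 per arm and inflation from 640 to 960. Without clustering, n = 2(1.96 + 1.2816)²/0.3² = 233.5, so 234 per arm. E5.c gives no cluster size. With the 80 PCPs of E4.d, 640/80 = 8 per PCP, the design effect is 1 + 7 × 0.02 = 1.14, and 234 × 1.14 gives 267. To obtain 320, about 19.4 patients per cluster are needed. The point here does not depend on this difference, but power before any bias does (step 4).

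**3. Formula**

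Let p be the missing fraction in an arm, and δ the mean amount by which its missing scores depart from what MAR predicts. A MAR analysis misses the full-data arm contrast by

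bias = p_PEAT × δ_PEAT − p_CDS × δ_CDS.

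All p and δ below are assumed.

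- One third missing in both arms, δ = 0.3 SD in PEAT and 0 in CDS: (1/3)(0.3) − 0 = 0.10 SD.
- δ = 0.3 SD in both arms, one third versus 20% missing: 0.10 − 0.06 = 0.04 SD.
- Equal δ and equal fractions: 0.

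**4. Consequence with one third missing**

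960/2 = 480 per arm, of whom 320 are observed. With 40 PCPs per arm that is 8 per PCP.

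- SE = √(2 × 1.14/320) = 0.0844 SD.
- Power at 0.3 SD without bias: Φ(0.3/0.0844 − 1.96) = 94%. The plan states 90%.
- Two-sided 5% error with 0.10 SD bias: 0.10/0.0844 = 1.185; P(Z > 0.775) + P(Z < −3.145) = 22.0%.
- Power with 0.10 SD bias towards the null: Φ(0.20/0.0844 − 1.96) = 65.9%.
- Tipping point for an estimate of 0.3 SD: lower 95% bound 0.3 − 1.96 × 0.0844 = 0.1346; divided by 1/3, this gives 0.40 SD.

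If clusters of 19.4 are used instead, so that power before bias matches the plan's 90%, the design effect is 1.368 and SE = √(2 × 1.368/320) = 0.0925. The three results become 19% error, 58% power and a tipping point of 0.36 SD.

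**5. Tipping point with 20% missing**

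480 × 0.8 = 384 observed, 384/40 = 9.6 per PCP, design effect 1 + 8.6 × 0.02 = 1.172, SE = √(2 × 1.172/384) = 0.0781. Then (0.3 − 1.96 × 0.0781)/0.2 = 0.73 SD. The extra variance from imputation is ignored in both tipping points.

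**6. Would the imputed versus non-imputed comparison reveal it?**

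Simulation with assumed variances, one third missing, δ = 0.3 SD in PEAT only, 20 imputations, 200 runs:

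| Analysis | Arm contrast (SD) |
|---|---|
| Full data | 0.090 |
| Likelihood on observed scores | −0.009 |
| Unshifted imputation | −0.009 |
| Imputation shifted by the true δ | 0.090 |

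The two MAR analyses differed by 0.005 SD on average, while both missed the full-data contrast by 0.099 SD. A second simulation made missingness depend on the outcome itself in one arm, with one third missing and a true effect of 0. The bias was −0.153 SD with imputation and −0.153 SD without. With the same mechanism in both arms it was −0.005 SD in each. Agreement between the two planned analyses is therefore not evidence against MNAR.

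**The case against.** The strongest reply is that the authors meant not missing completely at random. The check of whether non-respondents resemble respondents fits that reading, and imputation under MAR is then a legitimate response. This stands as far as it goes: the fault becomes a misworded trigger plus a missing robustness analysis. It does not supply that analysis.

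Second, the plan works to limit missing data: two phone calls to non-responders after baseline, reminder calls, monthly completeness checks and an interim look at missingness. It also collects other PROMIS scales and PHQ scores that could make MAR more plausible, although E7.b does not commit to using them in the imputation. All of this may shrink the problem. None of it shows how sensitive the result is to what remains.

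Third, it is partly an inference that both sides of the planned comparison assume MAR. If the non-imputed analysis deletes records with missing covariates, it rests on a different assumption. It still would not be an MNAR analysis.

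A reader might also take E4.d, where "approximately 30% will complete all of the questionnaires", to mean that 70% of data will be missing, and so infer a much larger bias. The text does not support that. The 30% is a share of 4,000 eligible patients, that is 1,200. Its complement mixes patients who never respond with patients who miss a single month. It is an upper bound on those missing at least one questionnaire and not a missing rate at any assessment. Results at 70% would also depend on an unknown base: 144 observed of 480 per arm, or 600 of 2,000, put the tipping point at about 0.09 or 0.25 SD. No result at 70% is relied on here.

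**Conclusion.** The point holds. As written, the rule in E7.b names a remedy that cannot do what is asked of it. On the milder reading the wording is wrong and an MNAR sensitivity analysis is still absent. It should be fixed before analysis.

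The size is conditional. With one third missing in each arm, 320 observed, 8 per PCP, ICC 0.02 and a 0.3 SD between-arm difference in departure, the bias is 0.10 SD. That gives about 22% error, or about 66% power if the bias is towards the null. An estimate of 0.3 SD would lose significance at a departure difference of about 0.40 SD, or about 0.73 SD with 20% missing. The missing fractions and departures are assumptions, and nothing was computed for CG-CAHPS.

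A reader might infer that the trial's result will be biased or that the primary model is invalid. The documents support neither. The mixed model is a sound primary analysis under MAR, and bias in the contrast needs departures or missing fractions that differ by arm. What is missing is a planned way to see how much that would matter.

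**What to change.** 1. Keep the mixed model on all observed scores as the primary analysis under MAR. Delete the trigger for imputation in E7.b, or correct it if not missing completely at random was meant.
2. Add a prespecified delta-adjusted (pattern-mixture) multiple-imputation sensitivity analysis for PROMIS Pain Interference. Vary the deltas separately by arm over a stated range and report the tipping point. The non-respondent calls could inform the range if they collect outcome scores, which E7.a does not say. Extend the analysis to CG-CAHPS only after defining which visit-triggered surveys count as missing.
3. As a minor clarification, say in E7.c that scores observed before a patient is lost to follow-up stay in the likelihood analysis. The present wording can be read as discarding them, which would weaken the MAR argument. Also say in E7.b whether imputing for respondents means partial responders only.

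The cost is a few lines of SAP text and modest extra analysis, with no new data if the deltas are a prespecified range. The downside is that the conclusion may read as less definitive.
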